8.6.2. Grade 1 or Grade 2 Toxicity/Adverse Event

Participants who develop a Grade 1 or Grade 2 AE or toxicity may continue study drug at the discretion of the investigator. Participants who choose to withdraw from the study due to a Grade 1 or 2 AE should have study withdrawal and follow-up evaluations completed.

Participants who develop ALT ≥ 3 times ULN while on study must consult with Medical Monitor prior to initiation or continuation of CAB LA + RPV LA

8.6.3. Grade 3 Toxicity/Adverse Event

Participants who develop a Grade 3 AE or toxicity should be managed as follows:

- If the Investigator has compelling evidence that the Grade 3 AE or toxicity has not been caused by IP, dosing may continue after discussion with the Medical Monitor.
- Participants who develop a Grade 3 AE or toxicity, which the Investigator considers related or possibly related to the IP, should have the IP withheld and be rechecked each week until the AE returns to Grade 2. Once the AE is Grade ≤ 2 , IP may be re-started.
- Should the same Grade 3 AE recur within 28 days in the same participant, the IP should be permanently discontinued and the participant withdrawn from study.
- Participants experiencing Grade 3 AEs requiring permanent discontinuation of IP should be followed weekly until resolution of the AE and to have withdrawal study evaluations completed. A follow-up visit should be performed 4 weeks after the last dose of IP. Any participant receiving at least one dose of CAB LA and/or RPV LA who discontinue IP / Withdraw will initiate treatment with HAART and enter the LTFU Phase for 52 weeks of follow up.
- Participants with Grade 3 asymptomatic laboratory abnormalities should be investigated for all potential non-drug related causes, and, following discussion with the Medical Monitor, may continue IP if the Investigator has compelling evidence that the toxicity is not related to IP, with the exception of liver chemistry stopping criteria (See Section 8.7.1). Isolated Grade 3 lipid abnormalities do not require withdrawal of IP.

8.6.4. Grade 4 Toxicity/Adverse Event

- Participants who develop a Grade 4 AE or toxicity must have IP permanently discontinued. However, if the Investigator has compelling evidence that the AE is not causally related to the IP, dosing may continue after discussion with, and assent from, the Medical Monitor. Participants should be rechecked each week until the AE returns to Grade 2.
- Participants experiencing Grade 4 AEs requiring permanent discontinuation of IP should be followed weekly until resolution of the AE and encouraged to complete the withdrawal and follow-up study evaluations as noted above. Any participant receiving at least one dose of CAB LA and /or RPV LA who discontinue IP /

Withdraw will initiate treatment with HAART and enter the LTFU Phase for 52 weeks of follow up.

- Participants with Grade 4 asymptomatic laboratory abnormalities should be investigated for all potential non-drug related causes, and, following discussion with the Medical Monitor, may continue therapy if the Investigator has compelling evidence that the toxicity is not related to IP, with the exception of liver chemistry stopping criteria (See Section 8.7.1). An in-clinic follow-up visit will be performed approximately 4 weeks after the last dose of study medication if AEs, SAEs, or laboratory abnormalities considered potentially harmful to the participant are ongoing at the last on-study visit. Isolated Grade 4 lipid abnormalities do not require withdrawal of IP.

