- Renal toxicity is met and no compelling alternate cause is identified;
- Corrected QT interval (QTc) >550 msec from three or more tracings separated by at least 5 minutes and considered causally related to IP. *Note: ECGs are not routinely conducted in this study.*
- Grade 4 clinical AE considered causally related to study drug;
- Participant has a Grade 3 or higher rash or Grade 2 rash with evidence of systemic involvement and no compelling alternative cause is identified
- Pregnancy (intrauterine), regardless of termination status of pregnancy.
- Participant withdrew consent

Efficacy data for participants withdrawing from the study will be considered evaluable up to the point at which they are withdrawn using the same criteria for evaluability as for participants who complete the study.

Safety data for all participants who receive any amount of study drug, including participants who withdraw from the study, will be included in evaluations of safety.

If a participant is prematurely or permanently withdrawn from the study, the procedures described in the Time and Events Table for the in-clinic Withdrawal visit are to be performed. An in-clinic Follow-Up visit will be conducted 4 weeks after the last dose of study medication for participants with ongoing AEs, and serious adverse events (SAEs) related & not related to study drug and also any laboratory abnormalities that are considered to be AEs or potentially harmful to the participant, at the last on-study visit.

All data from the Withdrawal visit will be recorded, as they comprise an essential evaluation that should be done prior to discharging any participant from the study.

The following actions must be taken in relation to a participant who fails to attend the clinic for a required study visit:

- a. The site must attempt to contact the participant and re-schedule the missed visit as soon as possible.

- b. The site must counsel the participant on the importance of maintaining the assigned visit schedule and ascertain whether or not the participant wishes to and/or should continue in the study.
- c. In cases where the participant is deemed ‘lost to follow up’, the investigator or designee must make every effort to regain contact with the participant (where possible, 3 telephone calls and if necessary a certified letter to the participant’s last known mailing address or local equivalent methods). These contact attempts should be documented in the participant’s medical record.

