8.7.2. Diarrhea

Participants with Grade 1 or 2 diarrhea may continue study intervention without interruption. Participants with diarrhea of any toxicity grade may be treated symptomatically with anti-motility agents; however, the recommended daily dose of the chosen anti-motility agent must not be exceeded. If symptoms persist or get worse on the recommended daily dose of the chosen anti-motility agent, then the anti-motility agent must be discontinued and consultation made with the Medical Monitor.

For participants with Grade ≥ 3 diarrhea that is unresponsive to the recommended dose of the anti-motility agents and for which an alternative etiology (e.g., infectious diarrhea) is not established, the treatment with the anti-motility agent and IP must be interrupted until resolution of diarrhea to Grade ≤ 2 or Baseline, after which IP and background ART may be resumed after discussion and agreement with the Medical Monitor. If Grade ≥ 3 diarrhea recurs within 28 days upon the resumption of IP, the IP should be permanently discontinued and the participant withdrawn from the study. Any participant receiving at

least one dose of CAB LA and /or RPV LA who discontinue IP / Withdraw will initiate treatment with HAART and enter the LTFU Phase for 52 weeks of follow up.

If loperamide is used for treatment of diarrhea, local prescribing information should be followed with respect to dose and frequency of administration. Loperamide dosing should not exceed local prescribing information.

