8.7.5. Creatine Phosphokinase (CPK) Elevation

A Grade 3 or higher elevation in CPK should result in a repeat assessment within 2-4 weeks to ensure the result is transient or due to exercise and will not require a change in study intervention. A history regarding use of drugs known to cause increase of CPK (such as statins) physical activity or exercise preceding the CPK evaluation should be obtained.

Grade 4 elevations in CPK should have a repeat assessment after the participant has abstained from exercise for >24 hours. For persistent Grade 4 CPK elevations that are considered possibly or probably related to the IP, IP should be discontinued and the participant withdrawn from the study. Any participant receiving at least one dose of CAB LA and/or RPV LA who discontinue IP / Withdraw will initiate treatment with HAART enter the LTFU Phase for 52 weeks of follow-up.

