8.7.6. Lipase Elevations and Pancreatitis

Participants with asymptomatic Grade 1 or 2 elevations in lipase may be followed closely for the development of symptoms.

Participants with asymptomatic Grade ≥ 3 elevations in lipase that are considered possibly or probably related to IP should have IP interrupted until serum lipase returns to Grade ≤ 2 . The lipase assay should be repeated within 2 weeks of any Grade ≥ 3 result. Participants with persistence of Grade ≥ 3 lipase in the absence of other diagnoses or reoccurrence of lipase elevation (at Grade ≥ 2) following reintroduction of IP should permanently discontinue IP.

Participants with a confirmed diagnosis of clinical pancreatitis that is considered possibly or probably related to IP should have IP held. After complete resolution of the episode, participants may be re-challenged with IP after discussion with the Medical Monitor, only if the Investigator has compelling evidence that the event was not caused by IP. Upon re-challenge, lipase determinations should be performed every 2 weeks for at least 6 weeks after re-initiation of treatment. With any elevation of lipase of Grade ≥ 2 or any recurrence of symptoms, the participant should discontinue IP and be withdrawn from study.

Any participant receiving at least one dose of CAB LA and/or RPV LA who discontinue IP / Withdraw will initiate treatment with HAART and enter the LTFU Phase for 52 weeks of **follow up**.

Drug Restart Following Transient Resolving Liver Events Not Related to Study Drug

Approval by VSLC for drug restart can be considered where:

Liver chemistries have a clear underlying cause (e.g., biliary obstruction, hypotension, and liver chemistries have improved to normal or are within $1.5 \times$ baseline and ALT $< 3 \times$ ULN). Ethics Committee or IRB approval of drug restart must be obtained, as required.

If restart of drug is approved by VSLC in writing, the participant must be provided with a clear description of the possible benefits and risks of drug administration, including the possibility of recurrent, more severe liver injury or death.

The participant must also provide signed informed consent specifically for the restart. Documentation of informed consent must be recorded in the study chart.

Study drug must be administered at the dose specified by VSLC.

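### Section 8.7.6 contradicts the Grade 4 stop in 8.6.4 for related asymptomatic lipase, and 8.7.2 permits resumption after Grade 4 diarrhoea

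*Protocol*

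**What the plan says.** Protocol 8.6.4 sets the rule by grade: "Participants who develop a Grade 4 AE or toxicity must have IP permanently discontinued". Dosing may continue only if the investigator has compelling evidence that the event was not caused by study drug and the Medical Monitor assents. A separate bullet applies the compelling-evidence test to asymptomatic Grade 4 laboratory abnormalities. Two exceptions are named. Liver chemistry is referred to 8.7.1, and "Isolated Grade 4 lipid abnormalities do not require withdrawal of IP".

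Protocol 8.7.6 deals with lipase. Asymptomatic elevations of Grade 3 or above "that are considered possibly or probably related to IP should have IP interrupted until serum lipase returns to Grade" 2 or lower. Permanent discontinuation is reserved for participants whose Grade 3 or higher value persists without another diagnosis, or whose lipase rises again: those who relapse "following reintroduction of IP should permanently discontinue IP".

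Protocol 8.7.2 deals with diarrhoea of Grade 3 or above that does not respond to anti-motility agents and has no established alternative cause. Study drug is interrupted until Grade 2 or baseline, "after which IP and background ART may be resumed after discussion and agreement with the Medical Monitor". A permanent stop follows only if diarrhoea of Grade 3 or above recurs within 28 days.

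Section 7 lists among the mandatory reasons for discontinuation a "Grade 4 clinical AE considered causally related to study drug".

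**The concern.** Grade 3 or above includes Grade 4, so 8.7.6 and 8.7.2 both reach events that 8.6.4 also governs, and they prescribe a different action.

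Both possible errors have a cost. If 8.7.2 is followed after a related Grade 4 diarrhoea, a participant may be redosed after an event that the grading table in Appendix 3 defines by danger to life. In the injectable arm that dose cannot be taken back: Section 6.8.1 notes that both long-acting drugs may be measurable for more than a year. If 8.6.4 is followed for an asymptomatic lipase value that has resolved, a participant loses a regimen that may be working and moves to oral HAART with 52 weeks of long-term follow-up.

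The choice also feeds a secondary endpoint, the proportion discontinuing treatment because of adverse events. Two participants with the same event could be counted differently.

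**Working it through.** The plan states no figure on this point, so the check sets the sections side by side.

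1. **Lipase.** Take an asymptomatic lipase value of at least 5.0 x ULN (Grade 4 in Appendix 3), judged possibly related. A judgement of possibly related rules out compelling evidence of no relation, so the 8.6.4 exception is closed and its action is a permanent stop. The 8.7.6 action is to interrupt until lipase is below 3.0 x ULN (the upper edge of Grade 2), then reintroduce. These cannot both be done. The value cannot be moved outside 8.6.4 as a laboratory finding only, because 8.6.4 has a bullet for exactly that class. Clinical pancreatitis does not share the problem, since 8.7.6 itself requires compelling evidence before re-challenge.

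2. **Diarrhoea.** Take unresponsive Grade 4 diarrhoea, no alternative cause found, later improved to Grade 2. Under 8.6.4 the stop is permanent unless the event is compellingly unrelated. Under Section 7 the stop is mandatory if the event is considered causally related. Under 8.7.2 resumption is allowed with Medical Monitor agreement. Because 8.7.2 permits and does not require, not resuming satisfies all three. The defect is a permission that two other sections withhold.

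3. **Origin of the 8.7.2 wording.** Section 8.6.3, for related Grade 3 events, withholds drug, allows restart at Grade 2 or lower, and stops permanently if the same Grade 3 event recurs within 28 days. Section 8.7.2 has the same structure, which suits a Grade 3 scope better than a Grade 4 one.

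4. **Precedence.** Section 8.6.1 introduces the grade rules as general guidance and, for oral dosing, foresees restart within 14 days unless Grade 3 or 4 toxicity persists. The title of 8.7 refers to specific toxicities, but its opening line calls the content general guidelines. The DTG + RPV risk table in 2.3.1 points to 8.7.5 for CPK and to 8.7.7 for renal function; the risk tables have no row for lipase or diarrhoea. No sentence says whether 8.7.6 or 8.7.2 overrides 8.6.4, or the reverse.

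**The case against.** The strongest reply is that the specific rule displaces the general one. Section 8.6.1 presents the grade rules as general, Section 7 allows temporary interruption to manage toxicity, and its mandatory Grade 4 line covers clinical events only, which fits with laboratory values following 8.7. For lipase there are safeguards: drug is held, the assay is repeated within 2 weeks, and persistence or relapse ends treatment. For diarrhoea, lacking an established alternative cause is not the same as being judged causally related, and resumption needs the Medical Monitor's agreement. Section 6.8 requires every resumption to be discussed with the Medical Monitor in advance.

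Much of this stands. It makes 8.7.6 a plausible statement of intent for lipase, and it shows that diarrhoea is not an outright contradiction. It does not remove the point. Where 8.6.4 means to make an exception it names it, as for isolated lipids and liver chemistry; lipase and diarrhoea are not named. Section 8 also bars waivers except for immediate safety concerns, so an unstated override is a weak basis for setting aside a mandatory stop. The Medical Monitor is asked to agree without being told which rule applies.

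A reader might infer that CPK and eGFR conflict in the same way, making four toxicities. The documents do not support that. Section 8.7.5 asks for a history of exercise and of drugs that raise CPK, and a repeat value after abstaining from exercise, which is largely the search for non-drug causes that 8.6.4 requires. It also ends in a stop: "For persistent Grade 4 CPK elevations that are considered possibly or probably related to the IP, IP should be discontinued". Every eGFR fall above 50% is Grade 4 (the grading table starts at 50%), but 8.7.7 withholds drug, requires Medical Monitor contact and considers restart only after weighing confounders. Section 7 separately mandates a stop when "Renal toxicity is met and no compelling alternate cause is identified". With the pointers in 2.3.1, these are at most minor tensions.

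**Conclusion.** The point holds for two toxicities: a direct contradiction for asymptomatic Grade 4 lipase judged possibly or probably related, and a permission contrary to 8.6.4 (and to Section 7 when the event is causally related) for Grade 4 diarrhoea.

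No incidence can be computed, because the documents give no rate for either event. Few cases are expected. Participants have taken oral CAB + RPV through at least LATTE Week 300, and Section 5.2 excludes verified Grade 4 laboratory abnormalities in the last 6 months of LATTE and ongoing or clinically relevant pancreatitis. With about 100 participants, one case handled differently moves the overall proportion discontinuing by 1/100 = 1.0 percentage point; that is true of any single participant and says nothing about how often it would happen.

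A reader might also infer a threat to the primary result. The documents do not support that. Protocol 10.1 plans no hypothesis test, and SAP Appendix 9 classes a safety withdrawal with no viral load in the window as having no virologic data, not as HIV-1 RNA at or above 50 c/mL. What is affected is participant safety and consistent handling of discontinuations due to adverse events. That justifies a correction at the next amendment.

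**What to change.** Two text edits.

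(1) In 8.7.2, limit the interrupt-and-resume wording to Grade 3 and add that Grade 4 diarrhoea follows 8.6.4 and Section 7. The instruction to stop the anti-motility agent, and the recurrence clause, should continue to cover both grades.

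(2) In 8.6.4, add one sentence stating that asymptomatic Grade 4 lipase is managed under 8.7.6. If the clinical team prefers the strict rule, limit the interrupt-and-reintroduce rule in 8.7.6 to Grade 3 instead. Either choice removes the contradiction, and it is a clinical decision.

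Section 7, 8.7.5 and 8.7.7 can stay as they are. There are no new assessments and no change to any endpoint or analysis. The downside is that edit (1) removes the option to restart after Grade 4 diarrhoea unless the event is compellingly unrelated to study drug.

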8.7. Specific Toxicities/Adverse Event Management

General guidelines for the management of specific toxicities that are considered to be associated with treatment of HIV participants.

Participants who permanently discontinue study drug for reasons of toxicity should be followed weekly until resolution of the AE and encouraged to complete the withdrawal and Follow-up study evaluations as noted in Section 8.5.3.

8.7.1. Liver Chemistry Stopping and Follow-up Criteria

Liver chemistry threshold stopping criteria have been designed to assure participant safety and to evaluate liver event etiology during administration of study drug and the follow-up phase. All Phase 3 participants who meet liver stopping criteria will be adjudicated by the ViiV Safety and Labelling Committee (VSLC) – resulting in a case summary, adjudication, and management plan. The VSLC contains an external expert hepatologist, familiar with both DILI and cabotegravir, who will participate in this review. This committee meets on a 3-weekly basis, and can be convened on an ad hoc basis as needed.

8.7.2. Diarrhea

Participants with Grade 1 or 2 diarrhea may continue study intervention without interruption. Participants with diarrhea of any toxicity grade may be treated symptomatically with anti-motility agents; however, the recommended daily dose of the chosen anti-motility agent must not be exceeded. If symptoms persist or get worse on the recommended daily dose of the chosen anti-motility agent, then the anti-motility agent must be discontinued and consultation made with the Medical Monitor.

For participants with Grade ≥ 3 diarrhea that is unresponsive to the recommended dose of the anti-motility agents and for which an alternative etiology (e.g., infectious diarrhea) is not established, the treatment with the anti-motility agent and IP must be interrupted until resolution of diarrhea to Grade ≤ 2 or Baseline, after which IP and background ART may be resumed after discussion and agreement with the Medical Monitor. If Grade ≥ 3 diarrhea recurs within 28 days upon the resumption of IP, the IP should be permanently discontinued and the participant withdrawn from the study. Any participant receiving at

least one dose of CAB LA and /or RPV LA who discontinue IP / Withdraw will initiate treatment with HAART and enter the LTFU Phase for 52 weeks of follow up.

If loperamide is used for treatment of diarrhea, local prescribing information should be followed with respect to dose and frequency of administration. Loperamide dosing should not exceed local prescribing information.

8.7.3. Hypertriglyceridemia/ Hypercholesterolemia

Samples for lipid measurements **must** be obtained in a fasted state according to the Time and Events table (Section 8.1). Participants who experience asymptomatic triglyceride or cholesterol elevations may continue to receive IP. Clinical management of participants with hypertriglyceridemia/hypercholesterolemia should **not** be based upon non-fasting samples (obtained in the fed state). A confirmatory fasting triglyceride and/or cholesterol level should be obtained prior to the institution of medical therapy for hyperlipidemia. Isolated Grade 3 and Grade 4 lipid abnormalities do not require withdrawal of IP.

Please see the Recommendations of the Adult AIDS Clinical Trial Group Cardiovascular Disease Focus Group [Dube, 2003] for full discussion of management of hyperlipidemia in the context of HIV therapy.

8.7.4. Seizures

Four cases of seizures have occurred in the CAB program cumulatively through 04 May 2018.

ViiV Healthcare has reviewed these cases in detail and does not believe they constitute a reasonable likelihood of causation associated with CAB. This assessment is supported by the lack of preclinical signal, class effect or known central nervous system (CNS) mechanism, the relatively low frequency of seizures relative to expected rates in both healthy and HIV positive participants and clinical confounders in each case. The Sponsor considers the risk of developing seizures on the study as being no higher than that of the rest of the HIV-1 infected population.

Seizures that occur on study should be managed according to the local guidelines on emergency seizure management which may include treatment with benzodiazepines, general supportive treatment, exclusion of metabolic and toxicological abnormalities using laboratory tests, septic workup and excluding underlying structural abnormalities with neuroimaging.

Where seizures occur, the Sponsor would like to better characterize these occurrences to enable systematic analyses.

Investigators are requested to document and report seizure or possible seizure events promptly (within 24 hours of learning of the event) to the Sponsor for evaluation and onward reporting. Data should be documented on the appropriate eCRF seizure page.

